4.6.2 Study Treatment Discontinuation

Patients must discontinue study treatment (but will continue to receive tumor assessments) if they experience any of the following:

- Intolerable toxicity related to study treatment
- Myocarditis of any grade
- Any medical condition that may jeopardize the patient's safety if he or she continues on study treatment
- Use of another systemic anti-cancer therapy (see Section [4.4.2](#))
- Pregnancy
- Radiographic disease progression per RECIST v1.1

[figure not shown]
Exception: Patients will be permitted to continue atezolizumab after RECIST v1.1 criteria for progressive disease are met if they meet all of the following criteria (see [Figure 3](#) for schematic representation):

- Evidence of clinical benefit (defined as the stabilization or improvement of disease-related symptoms) as assessed by the investigator
- Absence of symptoms and signs (including worsening of laboratory values [e.g., new or worsening hypercalcemia]) indicating unequivocal progression of disease
- No decline in ECOG performance status that can be attributed to disease progression
- Absence of tumor progression at critical anatomical sites (e.g., leptomeningeal disease) that cannot be readily managed and stabilized by protocol-allowed medical interventions prior to repeat dosing

Patients who demonstrate confirmed radiographic disease progression may be considered for continued study treatment at the discretion of the investigator, provided they continue to meet all the criteria above

The primary reason for study treatment discontinuation should be documented on the appropriate eCRF. Patients who discontinue study treatment prematurely will not be replaced.

Figure 3 Conditions for Continuing Atezolizumab in the Presence of Increased Radiographic Tumor Size

ECOG PS, Eastern Cooperative Oncology Group performance status; ICF, Informed Consent Form; RECIST v1.1, Response Evaluation Criteria in Solid Tumors, Version 1.1.

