 NX  N0  N1  N2  N3	REGIONAL LYMPH NODES (N) Regional lymph nodes cannot be assessed No regional lymph node metastasis Metastasis in ipsilateral peribronchial and/or ipsilateral hilar lymph nodes and intrapulmonary nodes, including involvement by direct extension Metastasis in ipsilateral mediastinal and/or subcarinal lymph node(s) Metastasis in contralateral mediastinal, contralateral hilar, ipsilateral or contralateral scalene, or supraclavicular lymph nodes)	 NX  N0  N1  N2  N3
 M0  M1  M1a  M1b	DISTANT METASTASIS (M) No distant metastasis (no pathologic M0; use clinical M to complete stage group) Distant metastasis Separate tumor nodule(s) in a contralateral lobe; tumor with pleural nodules or malignant pleural (or pericardial) effusion** Distant metastasis (in extrathoracic organs)	 M1  M1a  M1b

*Most pleural (and pericardial) effusions with lung cancer are due to tumor. In a few patients, however, multiple cytologic examinations of pleural (pericardial) fluid are negative for tumor, and the fluid is nonbloody and is not an exudate. Where these elements and clinical judgement dictate that the effusion is not related to the tumor, the effusion should be excluded as a staging element and the patient should be classified as M0.

Appendix 9

Risks Associated with Atezolizumab and Guidelines for Management of Adverse Events Associated with Atezolizumab

Toxicities associated or possibly associated with atezolizumab treatment should be managed according to standard medical practice. Additional tests, such as autoimmune serology or biopsies, should be used to evaluate for a possible immunogenic etiology.

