Although most immune-related adverse events observed with immunomodulatory agents have been mild and self-limiting, such events should be recognized early and treated promptly to avoid potential major complications. Discontinuation of atezolizumab may not have an immediate therapeutic effect, and in severe cases, immune-related toxicities may require acute management with topical corticosteroids, systemic corticosteroids, or other immunosuppressive agents.

The investigator should consider the benefit–risk balance a given patient may be experiencing prior to further administration of atezolizumab. In patients who have met the criteria for permanent discontinuation, resumption of atezolizumab may be considered if the patient is deriving benefit and has fully recovered from the event. Patients can be re-challenged with atezolizumab only after approval has been documented by both the investigator (or an appropriate delegate) and the Medical Monitor.

DOSE MODIFICATIONS

There will be no dose modifications for atezolizumab in this study.

TREATMENT INTERRUPTION

Atezolizumab treatment may be temporarily suspended in patients experiencing toxicity considered to be related to study treatment. If corticosteroids are initiated for treatment of the toxicity, they must be tapered over ≥ 1 month to the equivalent of ≤ 10 mg/day oral prednisone before atezolizumab can be resumed. If atezolizumab is withheld for > 12 weeks after event onset, the patient will be discontinued from atezolizumab. However, atezolizumab may be withheld for > 12 weeks to allow for patients to taper off corticosteroids prior to resuming treatment. Atezolizumab can be resumed after being withheld for > 12 weeks if the Medical Monitor agrees that the patient is likely to derive clinical benefit. Atezolizumab treatment may be suspended for reasons other than toxicity (e.g., surgical procedures) with Medical Monitor approval. The investigator and the Medical Monitor will determine the acceptable length of treatment interruption.

MANAGEMENT GUIDELINES

PULMONARY EVENTS

Dyspnea, cough, fatigue, hypoxia, pneumonitis, and pulmonary infiltrates have been associated with the administration of atezolizumab. Patients will be assessed for

pulmonary signs and symptoms throughout the study and will have computed tomography (CT) and/or magnetic resonance imaging (MRI) scans of the chest performed at every tumor assessment.

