Immune-related myocarditis has been associated with the administration of atezolizumab. Immune-related myocarditis should be suspected in any patient presenting with signs or symptoms suggestive of myocarditis, including, but not limited to, laboratory (e.g., B-type natriuretic peptide) or cardiac imaging abnormalities, dyspnea, chest pain, palpitations, fatigue, decreased exercise tolerance, or syncope. Immune-related myocarditis needs to be distinguished from myocarditis resulting from infection (commonly viral, e.g., in a patient who reports a recent history of gastrointestinal illness), ischemic events, underlying arrhythmias, exacerbation of preexisting cardiac conditions, or progression of malignancy.

All patients with possible myocarditis should be urgently evaluated by performing cardiac enzyme assessment, an ECG, a chest X-ray, an echocardiogram, and a cardiac MRI as appropriate per institutional guidelines. A cardiologist should be consulted. An endomyocardial biopsy may be considered to enable a definitive diagnosis and appropriate treatment, if clinically indicated.

Patients with signs and symptoms of myocarditis, in the absence of an identified alternate etiology, should be treated according to the guidelines in [Table 6](#).

Table 6 Management Guidelines for Immune-Related Myocarditis

Event	Management
Immune-related myocarditis, Grade 2	
 Withhold atezolizumab for up to 12 weeks after event onset^a and contact Medical Monitor. Refer patient to cardiologist. Initiate treatment as per institutional guidelines and consider antiarrhythmic drugs, temporary pacemaker, ECMO, or VAD as appropriate. Consider treatment with corticosteroids equivalent to 1–2 mg/kg/day IV methylprednisolone and convert to 1–2 mg/kg/day oral prednisone or equivalent upon improvement. If event resolves to Grade 1 or better, resume atezolizumab.^b If event does not resolve to Grade 1 or better while withholding atezolizumab, permanently discontinue atezolizumab and contact Medical Monitor.^c

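### Section 4.6.2 stops atezolizumab for myocarditis of any grade, but Appendix 9 Table 6 tells sites to resume after Grade 2 immune-related myocarditis, and no rule of precedence is given

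*Protocol*

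**What the plan says.** **Section 4.6.2.** The list opens: "Patients must discontinue study treatment (but will continue to receive tumor assessments) if they experience any of the following". One entry is "Myocarditis of any grade". It carries no condition on cause or on new onset. The only exception in the section concerns progression by RECIST v1.1.

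**Appendix 9, Table 6.** The text before the table sets its scope: "Patients with signs and symptoms of myocarditis, in the absence of an identified alternate etiology, should be treated according to the guidelines in" Table 6. The Grade 2 row begins "Withhold atezolizumab for up to 12 weeks after event onset", with contact to the Medical Monitor and referral to a cardiologist. It then says "If event resolves to Grade 1 or better, resume atezolizumab". A footnote requires any corticosteroids to be tapered first. Permanent discontinuation applies if Grade 2 does not resolve, and at Grade 3–4. There is no Grade 1 row.

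**Appendix 9, general re-challenge text.** Where treatment has been stopped for good, a way back is described: "resumption of atezolizumab may be considered if the patient is deriving benefit and has fully recovered from the event". It adds "Patients can be re-challenged with atezolizumab only after approval has been documented by both the investigator" and the Medical Monitor.

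**Section 5.1.2, flare rule.** For a patient whose existing autoimmune disease flares, dosing continues at Grade 1, is suspended at Grade 2 or 3 until the disease is stable, and ends at Grade 4.

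**Appendix 9, Table 10.** Myasthenia gravis and Guillain-Barré syndrome of any grade lead to permanent discontinuation.

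**Appendix 5** lists autoimmune myocarditis, myasthenia gravis and Guillain-Barré syndrome among the permitted histories.

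**The concern.** Immune-related myocarditis is a named risk of atezolizumab (Section 5.1.1), and myocarditis of Grade 2 or higher is an adverse event of special interest (Section 5.2.3). In a trial whose primary objective is long-term safety, sites need one instruction for it. As written, a site that follows Table 6 breaches a mandatory rule in Section 4.6.2, and Section 9.2 does not allow prospective requests to deviate. A site that follows Section 4.6.2 departs from the management guideline.

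The main stake is re-exposure of a patient with incompletely resolved myocarditis. A secondary one is consistent reporting. SAP Section 3.5.3 tabulates events leading to discontinuation separately from events leading to discontinuation or interruption, so the same case would enter the first table or not depending on the section the site had read.

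**Working it through.** No arithmetic applies. The check sets the current rules side by side by event and grade. All come from the protocol body and its appendices, not from the amendment summary.

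| Event | Section 4.6.2 | Appendix 9 | Section 5.1.2 flare rule | Result |
|---|---|---|---|---|
| Grade 2 immune-related myocarditis | Discontinue | Table 6: withhold, resume at Grade 1 or better | Not addressed unless a flare | Conflict |
| Grade 3–4 immune-related myocarditis | Discontinue | Table 6: permanently discontinue | Not addressed unless a flare | Dosing stops under both |
| Grade 1 flare of pre-existing autoimmune myocarditis | Discontinue | Table 6: no Grade 1 row | Maintain dosing | Conflict |
| Grade 1 flare of myasthenia gravis or Guillain-Barré syndrome, possibly drug-related | Not listed | Table 10: permanently discontinue | Maintain dosing | Conflict |
| The same flare, judged unrelated | Not listed | Outside the stated scope | Maintain dosing | No conflict |
| Grade 2–3 flare of these three diseases | Discontinue (myocarditis) | Table 10, if possibly related: permanently discontinue | Suspend until stable | All stop; restart conditions differ |

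Three routes to reconciling the first row were tried.

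1. **Different scope.** Table 6 covers myocarditis without another identified cause. That is a subset of what Section 4.6.2 covers, so every Table 6 Grade 2 case also falls under Section 4.6.2.
2. **The re-challenge text.** Suppose it is read into Section 4.6.2. It then demands full recovery and documented approval by two parties. The Table 6 Grade 2 row demands neither, and directs resumption at residual Grade 1, which Section 4.6.2 itself treats as a reason to stop.
3. **Precedence.** Section 5.1 names Section 5.1.2, Appendix 9 and the Investigator's Brochure together without ranking them. No protocol text ranks Section 4.6.2 against Appendix 9.

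Letting Table 6 govern wherever it speaks does not help either. With no Grade 1 row, Grade 1 myocarditis would fall to Section 4.6.2 and end treatment, while Grade 2 would permit a return to dosing.

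**The case against.** The strongest reply on Grade 2 myocarditis is that controls exist. Table 6 requires contact with the Medical Monitor when dosing is withheld, and Section 5.2.3 requires the event to reach the Sponsor within 24 hours. Section 4.6.2 is mandatory while the Appendix 9 text is guidance, so the wording favors stopping. Section 4.6.2 also says discontinue where Appendix 9 says permanently discontinue. If re-challenge is therefore open, a fully recovered patient with documented approval satisfies both rules. All of this stands, and it makes an unnoticed re-dosing less likely. It does not remove the conflict: the Grade 2 row still directs resumption at Grade 1 without approval, and contacting the Medical Monitor does not tell either party which text to apply.

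The reply on flares is stronger. Section 5.1.2 sends to Appendix 9 only specific events associated with atezolizumab, then gives flares their own rule. Appendix 9 opens with the same limit: "Toxicities associated or possibly associated with atezolizumab treatment should be managed according to standard medical practice". Table 11 in Section 5.3.4 names a preexisting condition as an example of another cause. A flare judged unrelated therefore follows Section 5.1.2 alone. What survives is the Grade 1 myocarditis flare, because Section 4.6.2 has no condition on cause, and the possibly related Grade 1 flare of myasthenia gravis or Guillain-Barré syndrome.

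A reader might go further and infer that the flare rule contradicts Appendix 9 throughout, for instance at Grades 2–3 or for hepatic, ocular, renal and skin disease. The documents do not support that. The scope limit applies there too. At Grades 2–3 of the three named diseases every rule stops dosing, and because the flare rule sets a condition for restarting rather than an order to restart, a site can comply by using the stricter test.

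**Conclusion.** The Grade 2 myocarditis conflict is established on the current text and is wrong as written. The flare conflict is real but secondary: it is limited to Grade 1 flares of three diseases, and for two of them it depends on a judgment that the drug may have contributed.

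No patient count can be derived. The group is probably small. Any patient could develop Grade 2 myocarditis, but the flare cases are narrowed further by Section 4.1.2, which requires controlled disease on unchanged treatment for 12 weeks, does not admit patients with serious or life-threatening immune-related histories, and excludes significant cardiovascular disease.

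It should not be inferred that the trial's statistics are affected. The sample-size table and the primary incidence analysis do not depend on this dosing decision; the only analysis touched is the discontinuation table noted above. Nor do the documents show that any patient was re-dosed against Section 4.6.2.

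The conclusion assumes that the Investigator's Brochure, cited in Sections 5.1 and 5.1.2 but not available here, contains no ranking of the rules. Even if it does, a mandatory protocol rule should not need an outside document to settle it.

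**What to change.** **Table 6, Grade 2 row.** Replace withhold-and-resume with the instruction already in the Grade 3–4 row, to discontinue permanently and contact the Medical Monitor. Keep footnote c, so that re-challenge needs full recovery and documented approval by the investigator and the Medical Monitor. The reverse change, limiting Section 4.6.2 to Grade 3–4, would also remove the contradiction, and the documents do not show which was intended. Aligning to the mandatory rule is the safer choice.

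**Section 5.1.2, flare rule.** Add one named exception: *except myocarditis, myasthenia gravis and Guillain-Barré syndrome of any grade, which follow Section 4.6.2 and Appendix 9.*

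A general sentence that the more restrictive instruction always applies is not recommended. It would turn Grade 3 ocular and renal flares from suspension into permanent discontinuation (Tables 5 and 12). Including controlled autoimmune disease is a stated aim (Section 1.3), so that trade-off would need its own justification. No hepatic example is needed.

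**Cost.** One table row, one clause and a letter to sites. A few more patients will stop, including some with Grade 1 flares who would now continue under Section 5.1.2. There is no statistical cost.

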4.6.3 Study and Site Discontinuation

The Sponsor has the right to terminate this study at any time. Reasons for terminating the study may include, but are not limited to, the following:

- The incidence or severity of adverse events in this or other studies indicates a potential health hazard to patients.
- Patient enrollment is unsatisfactory.

The Sponsor will notify the investigator if the Sponsor decides to discontinue the study.

The Sponsor has the right to close a site at any time. Reasons for closing a site may include, but are not limited to, the following:

- Excessively slow recruitment
- Poor protocol adherence
- Inaccurate or incomplete data recording
- Non-compliance with the International Conference on Harmonisation (ICH) guideline for Good Clinical Practice
- No study activity (i.e., all patients have completed the study and all obligations have been fulfilled)

5. ASSESSMENT OF SAFETY

5.1 SAFETY PLAN

The safety plan for patients in this study is derived from clinical experience with atezolizumab in completed and ongoing studies. The anticipated important safety risks are outlined below (see Section 5.1.1).

Measures will be taken to ensure the safety of patients participating in this study, including the use of carefully chosen inclusion and exclusion criteria and close monitoring of patients during the study. Administration of atezolizumab will be performed in a monitored setting in which there is immediate access to trained personnel and adequate equipment and medicine to manage potentially serious reactions.

After initiation of study treatment, all adverse events will be reported until 30 days after the last dose of study treatment or until initiation of new anti-cancer therapy, whichever occurs first. SAEs and adverse events of special interest will continue to be reported until 90 days after the last dose of study treatment or until initiation of new anti-cancer therapy, whichever occurs first.

Guidelines for managing anticipated adverse events, including criteria for dosage modification and treatment interruption or discontinuation, are provided below (Section 5.1.2), in [Appendix 9](#) and in the Atezolizumab Investigator's Brochure. Refer to Sections 5.2–5.6 for details on safety reporting during the study.

Patients with active infection are excluded from study participation. In the setting of a pandemic or epidemic, screening for active infections (including SARS-CoV-2) prior to and during study participation should be considered according to local or institutional guidelines or guidelines of applicable professional societies (e.g., American Society of Clinical Oncology or European Society for Medical Oncology).

Severe COVID-19 appears to be associated with a CRS involving the inflammatory cytokines IL-6, IL-10, IL-2, and IFN- γ (86). If a patient develops suspected CRS during the study, a differential diagnosis should include COVID-19, which should be confirmed or refuted through assessment of exposure history, appropriate laboratory testing, and clinical or radiologic evaluations per investigator judgment. If a diagnosis of COVID-19 is confirmed, the disease should be managed as per local or institutional guidelines.

5.1.1 Risks Associated with Atezolizumab

Atezolizumab has been associated with risks such as the following: IRRs and immune-related hepatitis, pneumonitis, colitis, pancreatitis, diabetes mellitus, hypothyroidism, hyperthyroidism, adrenal insufficiency, hypophysitis, Guillain-Barré syndrome, myasthenic syndrome or myasthenia gravis, meningoencephalitis, myocarditis, nephritis, myositis, and severe cutaneous adverse reactions. Immune-related reactions may involve any organ system and may lead to hemophagocytic lymphohistiocytosis (HLH) and macrophage activation syndrome (MAS), which are considered to be potential risks for atezolizumab. Refer to [Appendix 9](#) of the protocol and Section 6 of the Atezolizumab Investigator's Brochure for a detailed description of anticipated safety risks for atezolizumab.

5.1.2 Management of Patients Who Experience Specific Adverse Events

There will be no dose modifications for atezolizumab in this study.

Atezolizumab may be temporarily suspended in patients who experience toxicity considered to be related to study treatment. If atezolizumab is withheld for > 12 weeks after event onset, the patient will be discontinued from study drug. If the investigator believes the patient is likely to derive clinical benefit and the Medical Monitor is in agreement, atezolizumab can be resumed after being withheld for > 12 weeks after event onset.

If a patient must be tapered off steroids that have been used to treat adverse events, then atezolizumab may be withheld for more than 12 weeks after event onset until the steroids are discontinued or reduced to a prednisone dose (or dose equivalent) of \leq 10 mg/day. For patients with CNS metastases or autoimmune disease who require chronic steroid therapy, who have been receiving additional steroids to treat adverse events, and who now require a reduction in steroid dosage, atezolizumab may be withheld for more than 12 weeks after event onset until the steroid dosage has returned

to its baseline value. The investigator and the Medical Monitor will determine the acceptable length of treatment interruption.

Dose interruptions for reasons other than toxicity (e.g., surgical procedures) may be allowed with Medical Monitor approval. The investigator and the Medical Monitor will determine the acceptable length of treatment interruption.

Given the mechanism of action of atezolizumab, events associated with inflammation and/or immune-related adverse events (irAEs) have been closely monitored during the atezolizumab clinical program. Guidelines for the management of patients who experience specific adverse events associated with atezolizumab (i.e., pulmonary, hepatic, gastrointestinal, endocrine, ocular, infusion-related [IRR], pancreatic, dermatologic, neurologic, or autoimmune events) are provided in [Appendix 9](#) and Section 6 (Guidance for the Investigator) of the Atezolizumab Investigator's Brochure.

For patients developing a new autoimmune disease not listed in the Atezolizumab Investigator's Brochure, or for patients with an autoimmune disease who develop a flare, the following dosing guidance should be applied:

- Grade 1 event: atezolizumab dosage should be maintained
- Grade 2 or 3 event: atezolizumab should be suspended until the subject responds to treatment of the autoimmune disease and the disease becomes stable (see rules above regarding maximum suspended time). The subject should be referred to an appropriate specialist
- Grade 4 event: atezolizumab should be permanently discontinued and the subject should be referred to an appropriate specialist

